4.1.5 Blinding and procedures for unblinding

4.1.5.1 Blinding

Patients, investigators and everyone involved in trial conduct or analysis or with any other interest in this double-blind trial will remain blinded with regard to the randomised treatment assignments until after the data base lock (DBL) for the primary analysis. The randomisation code will be kept secret by Clinical Trial Support up to the interim database lock at Week 16.

The randomisation codes will be provided to bioanalytics prior to last patient completed to allow for the exclusion from the analyses of pharmacokinetic (PK) samples taken from placebo patients. Bioanalytics will not disclose the randomisation code or the results of their measurements until the trial is officially unblinded.

4.1.5.2 Unblinding and breaking the code

Emergency unblinding will be available to the investigator via IRT. It must only be used in an emergency situation when the identity of the trial drug must be known to the investigator in order to provide appropriate medical treatment or otherwise assure safety of trial participants. The reason for unblinding must be documented in the source documents and/or appropriate CRF page.

Due to the requirements to report Suspected Unexpected Serious Adverse Reactions (SUSARs), it may be necessary for a representative from BI's Pharmacovigilance group to access the randomisation code for individual patients during trial conduct. The access to the code will only be given to authorised Pharmacovigilance representatives and not be shared further.

4.1.6 Packaging, labelling, and re-supply

The investigational medicinal products will be provided by BI or a designated CRO. They will be packaged and labelled in accordance with the principles of Good Manufacturing Practice (GMP). Re-supply to the sites will be managed via an IRT system, which will also monitor expiry dates of supplies available at the sites. For details of packaging and the description of the label, refer to the ISF.

4.1.7 Storage conditions

Drug supplies will be kept in their original packaging and in a secure limited access storage area according to the recommended storage conditions on the medication label. A temperature log must be maintained for documentation.

Trial medication must be securely stored, e.g. in a locked refrigerator or at a pharmacy. If the storage conditions are found to be outside the specified range, the Clinical Trial Manager

(provided in the list of contacts) must be contacted immediately. Refer to the storage conditions for trial medications (STORM) document in the ISF for additional information.

The medication may only be dispensed to trial patients according to the Clinical Trial Protocol (CTP) by authorized personnel as documented in the trial staff list.

4.1.8 Drug accountability

The investigator or designee will receive the investigational drugs delivered by the sponsor when the following requirements are fulfilled:

- Approval of the clinical trial protocol by the Institutional Review Board (IRB) / ethics committee,
- Availability of a signed and dated clinical trial contract between the sponsor and the investigational site,
- Approval/notification of the regulatory authority, e.g. competent authority (CA),
- Availability of the curriculum vitae of the Principal Investigator,
- Availability of a signed and dated clinical trial protocol,
- Availability of the proof of a medical license for the Principal Investigator,
- Availability of FDA Form 1572 (if applicable).

Investigational drugs are not allowed to be used outside the context of this protocol. They must not be forwarded to other investigators or clinics.

The investigator or designee must maintain records of the product's delivery to the trial site, the inventory at the site, the use by each patient, and the return to the sponsor or warehouse / drug distribution centre or alternative disposal of unused products. If applicable, the sponsor or warehouse / drug distribution centre will maintain records of the disposal.

These records will include dates, quantities, batch / serial numbers, expiry ('use- by') dates, and the unique code numbers assigned to the investigational medicinal product and trial patients. The investigator or designee will maintain records that document adequately that the patients were provided the doses specified by the CTP and reconcile all investigational medicinal products received from the sponsor. At the time of return to the sponsor or appointed CRO, the investigator or designee must verify that all unused or partially used drug supplies have been returned by the clinical trial patient and that no remaining supplies are in the investigator's possession.

4.2 OTHER TREATMENTS, EMERGENCY PROCEDURES, RESTRICTIONS

4.2.1 Other treatments and emergency procedures

Stable doses of concomitant therapies for chronic conditions, for which neither the condition nor the treatment are judged to exclude the patient from participation (see Section [3.3](#)), are permissible. All concomitant medications should be carefully evaluated by the investigator and the Clinical Trial Manager should be contacted when there are questions regarding concomitant medications.

Proprietary confidential information © 2020 Boehringer Ingelheim International GmbH or one or more of its affiliated companies

During the trial, if the severity and progression of the disease worsens, the investigator can treat the patient with Standard of Care (SoC) of his/her choice. All efforts should be made to inform the patient of the importance of coming to the protocol specified visits (See [Flow Chart](#)) up to the EoS visit. Patients refusing to return to the study site for scheduled visits after the end of treatment should at least provide safety information by phone at the respective visits.

Overall, the choice of the escape treatment i.e Standard of Care treatment will be left at the discretion of the investigator. The sponsor will not provide/supply SoC treatment(s) to the sites. If a patient receives escape treatment the decision to maintain the patient on trial treatment will be decided with discussion between the investigator and sponsor.

4.2.2 Emergency procedures

Infusion reactions including anaphylactic reaction

In case of infusion reactions including anaphylactic reaction emerging during or after infusion of trial medication, the investigator should consider in accordance with severity of the reaction and local standard of care to:

- Immediately interrupt the infusion
- Treat with systemic anti-histamines, i.v. steroids, and in case of a severe allergic reaction (eg, anaphylactic reaction) epinephrine

Also draw a plasma sample for IgE and ADA as detailed in the Lab Manual (Central laboratory). Consider also the evaluation of histamine, serum tryptase, and complement components.

In case of infusion reaction, based on patient's clinical course and medical judgment, the infusion may be re-initiated in case of mild or moderate infusion reactions (according to Rheumatology Common Toxicity Criteria (RCTC) V2) at lower speed with gradual increase to complete the infusion as detailed in the Instructions for Preparation and Handling of BI 655130 in the ISF. In any case, the total duration of infusion should not exceed 180 minutes (3 hours).

In case of potential systemic allergic reaction, blood samples for determination of serum tryptase will be collected 0.5 h, 2 h, 6 h, 24 h after onset of the event.

In case of suspected drug related anaphylactic reaction (Appendix [10.1.1](#)) the investigator should discontinue treatment permanently with BI 655130.

Severe infections (according to RCTC V2), serious infections, opportunistic or mycobacterium tuberculosis infections.

Treatment of the infection should be initiated promptly according to local standard of care. No further trial medication should be administered until the active infection has resolved. Treatment with BI 655130 may be restarted when the patient has recovered according to investigator's assessment.

Overall, the choice of Standard of Care treatment will be left at the discretion of the investigator. The sponsor will not provide/supply SoC treatment (s) to the sites.

4.2.3 Restrictions

4.2.3.1 Restrictions regarding concomitant treatment

The medications (or classes of medications) listed in Table [4.2.3.1: 1](#) must not have been taken before inclusion for the time periods as specified, and are not permitted throughout the study participation.

Patients are prohibited from receiving the following therapies, during trial treatment and prior to Visit 2 for the duration specified in the Table below.

Patients who are re-allocated as Non-Responders at Visit 7 (Week 16) and have not reached a 50% reduction in EASI score compared to baseline at End of Treatment are prohibited from receiving the following therapies through to End of Study:

Table 4.2.3.1: 1 Restricted medications

Medication or class of medications^{1, 2}	Restriction duration prior to Visit 2
UVB phototherapy (including self-treatment with tanning beds or therapeutic sunbathing), PUVA	4 weeks
Hydroxyzine, diphenhydramine, doxepin ³	1 week
Any other topical medication than the provided emollient (e.g. moisturizers containing urea, calcineurin inhibitors, topical corticosteroids) ⁴	1 week
Azathioprine	4 weeks
Investigational products (including biologics)	30 days or 5 half-lives (whichever is longer)
IL36R inhibitors	before and during trial participation
All other biologics, including but not limited to: secukinumab (Cosentyx®) tildrakizumab (Ilumya®) rituximab, ustekinumab (Stelara®),	3 months or 5 half-lives (whichever is longer) 5.5 months prior to Visit 2 5 months prior to Visit 2 4 months prior to Visit 2

Medication or class of medications^{1,2}	Restriction duration prior to Visit 2
talizumab, alemtuzumab, guselkumab (Tremfya), ixekizumab (Taltz®), adalimumab (Humira®)	3 months prior to Visit 2
brodalumab (Siliq®), efalizumab, visilizumab, briakinumab, infliximab (Remicade®)	2 months prior to Visit 2
etanercept (Enbrel®)	6 weeks
live virus vaccinations	6 weeks
Any other systemic immunomodulating treatments (e.g. corticosteroids, cyclophosphamide), tofacitinib (Xeljanz®), apremilast (Otezla®)	30 days
Any systemic immunomodulating treatments for atopic dermatitis including JAK inhibitors, PDE4 inhibitors, systemic steroids	
retinoids	4 weeks no treatment initiation or dose escalation Must be discontinued prior to receiving the first dose of BI 65513/placebo

¹In case of disease worsening, the use of standard of care (physician's choice) is left at the discretion of the investigator (refer to Section [4.2.1](#)). Patient continuation on trial treatment will be reassessed based on the medication used for the disease worsening.

²This list is not all inclusive, for any medications that are not listed, contact the Clinical Trial Manager (CTM) for restriction duration

³ Other antihistamines for indications other than atopic dermatitis can be prescribed on an as-needed basis. Dose should, preferably, be stable within one week prior to V2 and during the course of the study.

⁴ No restriction on corticosteroid drops administered in the eye or ear; nasal corticosteroids to treat rhinitis;inhaled corticosteroids to treat asthma; Montelukast (systemic) to treat asthma or allergic rhinitis - if these medications were on stable maintenance dose for 3 months prior to Visit 2.

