3.1 OVERALL TRIAL DESIGN AND PLAN

This is a double-blind, placebo-controlled study assessing the safety, tolerability and efficacy of 600 mg BI 655130 compared to placebo given intravenously every 4 weeks in patients with moderate to severe atopic dermatitis. Safety and tolerability will be evaluated based on AE data collected and physical examination at every visit. At W16 patients will be evaluated for response to treatment by the change in EASI score compared to baseline. Patients who have responded, defined as having attained at least 75% reduction in EASI score compared to baseline will no longer receive treatment and will be followed at W 20, 24 and 28 to evaluate the sustainability of their response. If this patient reaches a 50% reduction in EASI score compared to baseline prior to the planned EOS at Week 28, they will immediately perform EOS and will be given the opportunity to receive treatment in an open label extension trial.

Patients who have not responded, defined as attained less than 75% reduction in EASI score compared to baseline will receive 600 mg BI 655130 at W16, 20, 24 and 28. Patients re-allocated to treatment, who reach EOS will be offered participation in the extension trial if they meet the eligibility criteria.

After re-allocation at Week 16, a patient will know what treatment they are on but will remain blinded to the treatment received until Week 16.

Figure 3.1.1 Trial design

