4.2.3.2 Restrictions on diet and life style

No specific restrictions on diet or life style of the patients are required. Patients should avoid prolonged exposure to sunlight and artificial UV light. Patients should only be using supplied emollient as instructed by the trial physician, instruction will be provided (see Section [6.2.2](#)).

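### Protocol Section 4.2.3.1 gives three different scopes for the restricted-medication ban after Week 16, and the visible SAP does not separate post-Week-16 efficacy data after other eczema therapy

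*Protocol*

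**What the plan says.** Three sentences in Protocol Section 4.2.3.1 introduce Table 4.2.3.1: 1.

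- The first covers every patient: the listed medications need a washout "and are not permitted throughout the study participation".
- The second reads "Patients are prohibited from receiving the following therapies, during trial treatment and prior to Visit 2", for the durations in the table. It is silent on time in the trial but off treatment.
- The third concerns only patients re-allocated as non-responders at Week 16 who are short of a 50% EASI reduction when treatment ends. They "are prohibited from receiving the following therapies through to End of Study".

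Topical steroids are on the list: "Any other topical medication than the provided emollient (e.g. moisturizers containing urea, calcineurin inhibitors, topical corticosteroids". Section 4.2.3.2 adds, with no time limit, "Patients should only be using supplied emollient as instructed by the trial physician".

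Section 4.2.1 and footnote 1 to the table separately let the investigator give standard of care of choice if the disease worsens.

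Under Section 3.1, patients with at least a 75% EASI reduction at Week 16 stop treatment and "will be followed at W 20, 24 and 28 to evaluate the sustainability of their response". Section 3.2 gives duration of response off treatment as the reason for this phase. A responder who falls back to a 50% reduction has the End of Study visit at once and is offered the extension trial.

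**The concern.** The follow-up of responders after Week 16 exists to show how long response lasts without drug. Whether other eczema therapy is allowed in that phase should be unambiguous, and the analysis should show who used it. As written, two sites could read the same section differently. One would record a responder's topical steroid as a restricted-medication deviation; the other would treat it as permitted. EASI at Weeks 20, 24 and 28, and the date on which a responder meets the exit level, could then reflect other therapy as well as persistence of the drug effect.

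The same uncertainty applies to non-responders who have reached a 50% reduction, from their last infusion at V10 until V11.

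**Working it through.** The question is mainly one of reading the text. The only arithmetic concerns the window.

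**The plan's own figure.** Flow chart footnote 18 puts the responders' End of Study visit 16 weeks after last treatment, no later than Week 28. From the flow chart days, the last blinded infusion is V6 (Day 85) and V10 is Day 197: (197 − 85)/7 = 16 weeks. The figure reproduces.

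**Window in doubt.**
- Responders: V7 (Day 113) to V10 (Day 197), (197 − 113)/7 = 12 weeks, with visits at Weeks 20, 24 and 28.
- Non-responders: V10 (Week 28) to V11 (Weeks 32 to 44), 32 − 28 = 4 to 44 − 28 = 16 weeks. This takes the end of treatment as the last infusion at V10.

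**Use of a listed therapy without disease worsening, by sentence followed.**

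| Group and period | First sentence | Second and third sentences |
|---|---|---|
| Responders, Weeks 16 to 28 | Banned | Not covered by the ban |
| Non-responders at 50% or better, V10 to V11 | Banned | Not covered by the ban |
| Non-responders below 50%, V10 to V11 | Banned | Banned |

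If the first sentence governs, the third adds nothing. If the second and third govern, the first is too wide.

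**Use on worsening.** Section 4.2.1 and footnote 1 allow standard of care in all three rows, whichever sentence is followed. The consequence they attach is a review of whether trial treatment continues, which has no effect on a responder already off drug.

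**What the visible SAP does with such use.**
- Table 6.2: 1, codes D2.01a to D2.01c, flags restricted medication that may influence efficacy and excludes no one. What counts as restricted after Week 16 depends on the sentence followed.
- Section 6.6.2 sets binary outcomes to missing after premature stopping of study medication. Starting another eczema therapy is not a trigger.
- Section 7.2 tabulates medication started on or after the Week 16 visit by ATC3 class and preferred name. Its dedicated table of atopic dermatitis medication covers the double-blind period only.
- Section 6.1 reports the re-allocation period separately and descriptively, with no split by other therapy.

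**Week 16 comparison.** Therapy started after the Week 16 assessment cannot change the Week 16 EASI.

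**The case against.** The best defence is that no sentence in Section 4.2.3.1 permits anything. A narrower ban does not cancel a wider one, so a site that follows the first sentence obeys all three, and the emollient-only instruction in Section 4.2.3.2 points the same way. SAP Section 6.1 also labels the whole re-allocation period an open-label treatment phase, including patients on no treatment, so the second sentence might be stretched to cover responders. Against this, Section 3.1 says that responders no longer receive treatment, and a separate sentence for one subgroup makes sense only if the others are not already covered. The Amendment 3 log describes the restriction as extended for non-responders, but a log is context and settles nothing. The text can be reconciled by choosing a reading, but it does not say which to choose.

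Three further objections stand and limit the point.

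- A reader might infer that the conflict lets a worsening responder be treated topically and still be counted as sustained. That can happen under every reading, because of the standard-of-care allowance. Reconciling the sentences would not prevent it; only the analysis can show it.
- A reader might infer that at V11 patients with the better outcome have access to other therapy and those with the worse outcome do not. That pattern needs the first sentence to be set aside, and it ignores the standard-of-care route open to patients who worsen.
- A reader might infer that sustained response cannot be attributed at all. Concomitant therapy is recorded at every visit and deviations are listed per patient, so users can be identified. Attribution is in any case limited because this phase is selected on response, open label and not re-randomised.

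**Conclusion.** The inconsistency is real and is in the current text. For responders over 12 weeks, and for non-responders at a 50% reduction after V10, the protocol does not say clearly whether listed therapies may be used without worsening, and the meaning of D2.01a to D2.01c shifts accordingly. Independently of that, standard of care on worsening is always allowed, and no visible SAP rule separates the later efficacy data. The summaries of sustainability and duration of response may therefore be confounded.

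The reach is modest. The listed primary and secondary efficacy endpoints stop at Week 16, later results are descriptive, and the Week 16 primary comparison is not affected.

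The documents give neither an expected EASI75 rate nor a rate of topical use, so the size of the effect cannot be estimated. If 20% to 40% of the 30 BI 655130 patients respond (6 to 12 patients, an assumption), one reclassified patient moves a proportion by 1/12 = 8 to 1/6 = 17 percentage points. A reader might take that for the size of the bias. It is only the step size of a small denominator and says nothing about how often such use would occur. The visible text also defines no proportion with sustained response at Week 28.

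The statement about the SAP holds for visible text only: Section 7.4.2 and further endpoint sections are redacted and may contain a handling rule.

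**What to change.** **Protocol.** Reconcile the three sentences of Section 4.2.3.1 so that one scope is stated for each group: responders from Week 16 to End of Study, and non-responders from V10 to V11, above and below the 50% level. Align D2.01a to D2.01c in SAP Table 6.2: 1 with the result. Which clinical scope applies is for the sponsor to decide.

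**SAP.** Unless a redacted section already does so, flag each responder who starts any eczema therapy from Table 4.2.3.1: 1 between Week 16 and End of Study, including standard of care for worsening, with its start date. Show the EASI and maintained-response summaries at Weeks 20 to 28 twice: regardless of such therapy, and without it.

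**Cost.** A wording clarification and one extra descriptive display from concomitant-medication data already collected. Fewer patients will count as sustained in the display without other therapy.

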4.2.3.2 Restrictions on diet and life style

No specific restrictions on diet or life style of the patients are required. Patients should avoid prolonged exposure to sunlight and artificial UV light. Patients should only be using supplied emollient as instructed by the trial physician, instruction will be provided (see Section [6.2.2](#)).

4.2.3.3 Contraception requirements

Women of childbearing potential (WOCBP) must use highly effective methods of birth control per ICH M3 (R2) that result in a low failure rate of less than 1% per year when used consistently and correctly. A list of contraception methods meeting these criteria is provided in the patient information.

Female Patients:

Acceptable methods of birth control for this trial are:

- Combined (estrogen and progestogen containing) hormonal birth control associated with inhibition of ovulation.
- Progestogen-only hormonal birth control associated with inhibition of ovulation.
- Intrauterine device (IUD) and intrauterine hormone-releasing system (IUS).
- Bilateral Tubal occlusion (blocking of the fallopian tubes).
- Vasectomy of sexual partner (proven effective by absence of sperm on the ejaculation).
- Complete sexual abstinence (not to have male-female vaginal sex).

As monoclonal antibodies can be secreted in milk, women should refrain from breastfeeding once they receive the study drug and up to 16 weeks after, i.e. until BI 655130 is eliminated. They can start nursing again after this period.

4.3 TREATMENT COMPLIANCE

Administration of the trial medication will be done in the study center under the supervision of the investigator or a designee. The measured plasma concentrations will provide additional confirmation of compliance.

5. ASSESSMENTS

5.1 ASSESSMENT OF EFFICACY

Efficacy will be assessed using standard criteria that have been used in numerous AD studies, including the Eczema Area and Severity Index (EASI), the scoring of atopic dermatitis (SCORAD), Investigator Global Assessment (IGA) and Dermatology Quality of Life Index (DLQI).

The primary efficacy endpoint for this trial is percent change in EASI Score at Week 16 compared to Baseline. Secondary endpoints include EASI 50, EASI 75, SCORAD and IGA. An interim analysis of change in EASI at Week 4 will be conducted when 75% of patients have completed the Week 4 visit. The details of these assessments are described below.

EASI

The EASI scoring system is based on the psoriasis area and severity index (PASI) used routinely in patients with psoriasis to describe signs and severity of the disease. The principle of integrating disease extent and severity to describe disease led to the definition of the EASI [R18-2665]. The EASI score assesses the extent of disease at four body sites and measures four clinical signs: (1) erythema, (2) induration/papulation, (3) excoriation, and (4) lichenification, each on a scale of zero to three. The EASI score confers a maximum of 72 and evaluates two dimensions of AD: disease extent and clinical signs. The suggested severity strata for the EASI are as follows: 0 = clear; 0.1–1.0 = almost clear; 1.1–7.0 = mild; 7.1–21.0 = moderate; 21.1–50.0 = severe; 50.1–72.0 = very severe [R18-2851]. The EASI score does not assess symptoms like pruritus and sleep loss [R18-2670].

SCORAD

The SCORAD index will also be included in the clinical trials and has three elements: extent of disease, disease severity and subjective symptoms. These combine to give a maximum possible score of 103. The commonly used SCORAD strata to classify AD severity are mild = 0–25, moderate = 26–50 and severe = 51–103 [R18-2664, R18-2679].

IGA

The IGA scale allows investigators to assess overall disease severity at one given time point, and it consists of a five-point severity scale from clear to severe disease (0= clear, 1 =almost clear, 2 = mild, 3 = moderate, 4= severe). The IGA scale uses clinical characteristics of erythema, infiltration, papulation, oozing and crusting as guidelines for the overall severity assessment [R18-2670].

DLQI

The DLQI is a patient-administered, ten-question, quality of life questionnaire that covers six domains including symptoms and feelings, daily activities, leisure, work and school, personal relationships and treatment [R05-2548]. The DLQI has a one-week recall period. Response categories include “not relevant” (score of 0), “not at all” (score of 0), “a little” (score of 1), “a lot” (score of 2) and “very much” (score of 3). Question 7 is a “yes”/ “no” question where “yes” is scored as 3. DLQI total score is calculated by summing the scores of each question resulting in a range of 0 to 30 where 0-1 = no effect on patient’s life, 2-5 = small effect, 6-10 = moderate effect, 11-20 = very large effect, and 21-30 = extremely large effect on patient’s life. The higher the score, the more the quality of life is impaired. A 4-point change from baseline is considered a clinically important difference [R18-1988].

